2 LIST OF ABBREVIATIONS

AE	Adverse event
AED	Antiepileptic drug
ALT	Alanine aminotransferase
AST	Aspartate aminotransferase
AUC	Area under the plasma concentration versus time curve
β -hCG	β -human chorionic gonadotropin
CBZ	Carbamazepine
CFR	Code of Federal Regulations
CNS	Central nervous system
C-SSRS	Columbia Suicide Severity Rating Scale
CT	Computed tomography
CYP	Cytochrome P450
DRESS	Drug reaction (or rash) with eosinophilia and systemic symptoms
EC	Ethics committee
ECG	Electrocardiogram
eCRF	Electronic case report form
EEG	Electroencephalograph
FDA	Food and Drug Administration
GABA	Gamma-aminobutyric acid
GCP	Good Clinical Practice
ICH	International Conference on Harmonisation
IND	Investigational new drug
IRB	Institutional review board
IWRS	Interactive Web response system
kg	Kilogram
mg	Milligram
MRI	Magnetic resonance imaging
PHI	Protected health information
PI	Principal Investigator
SAE	Serious adverse event
SKLSI	SK Life Science, Inc.
SUDEP	Sudden unexpected death in epilepsy
SUSAR	Suspected unexpected serious adverse reaction
VNS	Vagal nerve stimulator
VPA	Valproic acid (divalproex sodium)

3 STUDY ASSESSMENTS

Table 1. Study Assessment Flow Chart

4 BACKGROUND AND DOSE SELECTION

4.1 Introduction

This is a protocol for a human research study. This study is being conducted according to US and international standards of Good Clinical Practice (GCP) (Food & Drug Administration [FDA] Title 21 Part 312 and International Conference on Harmonisation [ICH] guidelines), applicable government regulations, and Institutional research policies and procedures.

4.2 Considerations for Studies of Epilepsy

According to the World Health Organization, epilepsy afflicts more than 50 million people worldwide.¹ Epilepsy leads to an increased risk of injury from accidents and an increased rate of mortality and has a significant impact on quality of life. First-generation antiepileptic drugs (AEDs) are still commonly used, even though they can produce a diversity of serious adverse events (SAEs). New AEDs approved since the early 1990s have shown an improved tolerability profile. Nonetheless, approximately 30% of epilepsy cases, particularly those with partial seizures, are refractory to treatment. Many of these patients are taking multiple antiepileptic drugs. It is important to understand any interaction that occurs between them as well as the long term safety profile of YKP3089 when given as adjunctive therapy.

Choice of add-on (adjunctive) design. The initial evaluation of a new antiepileptic drug generally includes a determination of its efficacy in reducing the frequency of seizures in adults who are refractory to treatment with other AEDs.^{2,3,4} Because of the risk of exacerbation of seizure severity and frequency upon withdrawal of long-term AED therapy, even in the refractory population, the new AED under study is added to the existing therapy instead of being used as monotherapy. Because partial seizures represent the most common type in both adults and children and claim a disproportionate share of medically refractory cases, they have been the most frequently selected seizure type in the investigation of new AEDs.

4.3 Background

4.3.1 YKP3089 Structure

YKP3089 is (R)-(+)-1-(2-chloro-phenyl)-2-tetrazol-2-yl-ethyl ester, which has the chemical formula $C_{10}H_{10}ClN_5$. YKP3089 is being provided in tablets that contain 50 or 100 mg of the active ingredient. It is a novel small molecule of molecular weight 267.68. Its structure is shown in Figure 1.

[figure not shown]

Figure 1. Structure of YKP3089

YKP3089 is a novel small molecule with open INDs for epilepsy (76,809), neuropathic pain (IND 108,178), and anxiety (IND 72,741). It is currently in Phase 2 of development as an antiepileptic agent for partial onset seizures. YKP3089 was shown to be active in standard animal models of epilepsy, neuropathic pain, and anxiety when administered orally.

4.4 Pharmacology

Receptor test systems have shown that YKP3089 does not show significant activity at any of the classical receptor types (eg, adrenergic, GABAergic) or pharmacologic receptors. However, *in vitro* electrophysiology assays showed YKP3089 to be an inhibitor of the slow inactivated state of sodium channels. YKP3089 may also increase inhibitory synaptic transmission by facilitating the release of GABA.

4.4.1 Absorption, Distribution, Metabolism, and Excretion

In vitro studies with human microsomes revealed that YKP3089 directly inhibited CYP2B6 (IC_{50} = 280 μ M), CYP2C19 (IC_{50} = 170 μ M), and CYP3A4/5 (as measured by testosterone 6 β -hydroxylation, IC_{50} = 890 μ M; and midazolam 1'-hydroxylation, IC_{50} = 720 μ M). These IC_{50}

the reciprocal effects of phenytoin and YKP3089, plasma phenytoin exposure increased with co-administration of YKP3089 by 67% (C_{max}) and 84% (AUC) and plasma YKP3089 exposure (C_{max} , AUC) decreased with co-administration of phenytoin by 27 - 28%. Preliminary results of a drug interaction study examining the reciprocal effects of phenobarbital and YKP3089, plasma phenobarbital exposure increased with co-administration of YKP3089 by 34% (C_{max}) and 37% (AUC) and plasma YKP3089 exposure (C_{max} , AUC) decreased with co-administration of phenobarbital by 10-15% based on historical controls.

4.4.2 *Safety Pharmacology and Toxicity Studies*

YKP3089 has been assessed in a large number of safety pharmacology and toxicology studies including single-dose toxicity, repeat-dose toxicity, cardiotoxicity, genetic toxicity, and reproductive toxicity studies in animals. Safety pharmacology studies showed that the doses that produced beneficial central nervous system (CNS) effects of YKP3089 in animal models do not result in obvious negative effects on the CNS. No evidence of cardiovascular effects was observed by telemetric electrocardiography in male monkeys.

Details of the preclinical safety and toxicity studies of YKP3089 can be found in the Investigator's Brochure. The most common AEs in preclinical studies of YKP3089 involved the central nervous system (CNS).

Reproductive toxicity studies showed adverse effects on reproductive performance when the dosage of YKP3089 was high enough to induce maternal toxicity, as evidenced by decreased food consumption and decreased body weight. However, there was no evidence of teratogenicity.

The results of standard genotoxicity studies of YKP3089 were negative. There is no evidence of carcinogenicity in standard testing of two rodent species.

4.4.3 *Clinical Safety and Efficacy*

Cumulatively, 953 subjects have been exposed to YKP3089 in a total of 14 Phase 1 and 3 Phase 2 clinical studies.

The results of the first completed double-blind, randomized, placebo-controlled trial in subjects with partial epilepsy demonstrated that treatment with 200 mg of YKP3089 produced a highly

statistically significant reduction in the frequency of partial onset seizures (Table 2) and seizure free rates (Table 3). YKP3089 was generally well-tolerated. The rate of adverse event withdrawals was similar between the YKP3089 and placebo groups. No life threatening serious adverse events were identified among YKP3089-treated subjects. The most common central nervous system adverse events in the YKP3089 group were somnolence, dizziness, fatigue, and gait disorder.

The second randomized, double-blind, placebo-controlled, dose response trial with a 18 week treatment period enrolled a total of 437 subjects, 108 in a 100 mg YKP3089 group, 110 in a 200 mg YKP3089 group, 111 in a 400 mg YKP3089 group and 109 in a placebo group. The trial confirmed that treatment with 200 mg/day and 400mg/day of YKP3089 produces a highly statistically significant reduction in the frequency of partial onset seizures in patients with partial epilepsy (Table 2) and high seizure free rates (Table 4).

Table 2: Effect Size of Median Percent Reduction and 50% Responder Rate Relative to Placebo in YKP3089 Trials

	YKP3089C013 Study	YKP3089C017 Study		
Dose	200mg	100mg	200mg	400mg
Median Percent Reduction	34.1	11.5	31.0	31.0
50% Responder Rate	28.2	19.0	35.2	38.7

P values in all comparisons were <0.01

Table 3: Seizure free Rates (Completer Population) at 200mg in YKP3089C013

Responder Type	6 Week Maintenance Phase		
	% Responders placebo N = 99	% Responders YKP3089 N = 102	P value
100%	9.1	27.5	0.0003

Table 4: Seizure Free Rates (Completer Population) in YKP3089C017

Responder Type	12 Week Maintenance Phase			
	% Responders	% Responders (YKP3089 100 mg)	% Responders	% Responders

There have been three cases of DRESS syndrome in YKP3089 clinical studies.

Rash and hypersensitivity During the YKP3089 development program there have been other reports of rash and hypersensitivity reactions, some resulting in hospitalization and/or discontinuation. An aggregate analysis of the rate of rash/hypersensitivity and DRESS in subjects exposed to multiple doses of YKP3089 was performed Table 5.

Table 5: Rate of rash/hypersensitivity and DRESS in subjects exposed to multiple doses of YKP3089

	Starting Dose 50 mg with 50 mg Increase Every 2 Weeks		Starting dose 50 mg with 50 mg Increase Every 1 Week		Starting dose 100 mg or more with 100 mg Increase Every 5 to 7 Days		Total	
	Active	Placebo	Active	Placebo	Active	Placebo	Active	Placebo
Subjects Exposed	120	112	363	152	350	37	833	301
Rash/hypersensitivity N (%)	1 (0.8%)	3 (2.7%)	18(5.0%)	4(2.6%)	19 (5.4%)	3 (8.1%)	38 (4.6%)	10 (3.3%)
Dropouts	1 (0.8%)	0	8 (2.2%)	1 (0.6%)	9 (2.5%)	0	18 (2.2%)	1 (0.3%)
DRESS	0	0	1	0	2	0	3	0

The results of the aggregate analysis suggest that lower YKP3089 starting dose and slower titration rate are associated with lower risk of rash/hypersensitivity.

- When YKP3089 dosing was increased weekly or faster, the rate of rash/hypersensitivity reactions was approximately 5%. When YKP3089 was increased by 50 mg increments every 2 weeks, only one case (0.8%) of hypersensitivity reactions was observed.

Two cases DRESS occurred when the first dose of YKP3089 was 100 mg (epilepsy study) or 200 mg (healthy volunteer) followed by rapid titration. The third case, in a healthy volunteer, occurred in a study where the initial dose of YKP3089 was 50 mg/day for 1 week followed by 50 mg weekly increments.

4.5 Rationale

4.5.1 *Study Rationale*

Approximately 30% of epilepsy cases, particularly those with partial seizures, are refractory to treatment. Many of these patients are taking multiple antiepileptic drugs. It is important to understand any interaction that occurs between them as well as the long term safety profile of YKP3089 when given as adjunctive therapy.

Based on healthy volunteer studies with phenytoin and phenobarbital, YKP3089 increases plasma levels of phenobarbital and phenytoin levels. A portion of this open label safety and pharmacokinetic study is designed to understand the impact of adding YKP3089 to an AED regimen including either phenytoin or phenobarbital in subjects with partial epilepsy.

In addition this open label and pharmacokinetic study will enroll subjects taking concomitant AEDs other than phenytoin or phenobarbital to study long term safety and obtain population pharmacokinetic data.

A review of the YKP3089 safety database confirmed three cases of DRESS syndrome among the 953 subjects exposed to the drug.

In order to further characterize the safety profile of YKP3089 while minimizing risk to patients, the following plan was developed:

1. Low starting dose (12.5 mg) and slower titration (dose increase every two weeks)
2. Close monitoring (visits every two weeks) during the first 4 months of treatment to allow early detection of suspected cases of hypersensitivity reaction
3. Evaluation of suspected cases of hypersensitivity reaction to facilitate accurate diagnosis
4. Care of subjects with hypersensitivity reactions to minimize consequences

4.5.2 *Dose Justification*

The target dose of 200 mg/day is based on the efficacy, safety, and tolerability of YKP3089 in previously completed and ongoing studies.

Initiating treatment with YKP3089 at 12.5 mg and then increasing the dose every two weeks is likely to further reduce the risk of many side effects including hypersensitivity reactions. Slowing the titration rates of pharmaceuticals is a well-known procedure for mitigating risk of adverse reactions. Reducing the initial dose and slowing the titration can reduce many central nervous system or gastrointestinal side effects. It has been demonstrated that lowering the initial dose and slowing the titration rate can mitigate the occurrence of rash and possibly the rate of more serious and potentially life threatening adverse cutaneous reactions (Zaccara G, 2007).

After initiating treatment with YKP3089 for two weeks at 12.5 mg and then for two weeks at 25mg YKP3089, subjects taking phenytoin or phenobarbital will titrate YKP3089 upward at a rate of 50mg every other week to a target dose of 200mg/day. This titration is appropriate for this portion of the study because of the known interactions between YKP3089 200mg and phenytoin and phenobarbital. Titrating by 50mg of YKP3089 every other week to steady state will allow better understanding of the clinical impact of any interaction and allow for dosage adjustment of phenytoin or phenobarbital.

Subjects taking concomitant AEDs other than phenytoin or phenobarbital will titrate YKP3089 upward at the same rate to a target dose of 200mg/day.

After reaching a target dose of 200mg, all subjects will be allowed to titrate up to a maximum dose of 400mg/day of YKP3089. A maximum dose of 400mg/day is justified by the additional efficacy seen in the subjects randomized to 400mg/day in the completed dose response study. Seizure free rate effect size in this group approached 20% during the maintenance phase.

4.6 **Potential Risks and Benefits**

Cumulatively, 953 subjects have been exposed to YKP3089 in a total of 14 Phase 1 and 3 Phase 2 clinical studies.

The potential risks in this study includes,

1. Phenytoin dose related toxicity
2. Risk of phenytoin hypersensitivity syndrome
3. Phenobarbital dose related toxicity
4. Rash / hypersensitivity related to YKP3089 exposure
5. DRESS syndrome related to YKP3089 exposure
6. YKP3089 dose related toxicities

Uncontrolled partial epilepsy is a life threatening disease with significant morbidity and elevated standard mortality rates.

The early signs and symptoms associated with hypersensitivity reaction that may progress to DRESS are readily identifiable by patients and clinicians. When detected and adequately managed, progression to DRESS can be prevented or reversed. The potential benefits of YKP3089 include significant partial seizure frequency reduction and substantial seizure free rates (~18%) in patients who continue to suffer seizures despite history of treatment with multiple AEDs. The current benefit/risk profile in conjunction with the risk minimization measures support the enrollment of partial epilepsy patients into this open-label study to assess the profile of YKP3089 as a potential antiepileptic drug

5 STUDY OBJECTIVES

The objective is to evaluate the safety and pharmacokinetics of YKP3089 and concomitant AEDs when administered as adjunctive therapy for the treatment of partial seizures. The evaluations will include:

1. Phenytoin-YKP3089 interaction
2. Phenobarbital-YKP3089 interaction
3. Long term safety of YKP3089 as adjunctive therapy in subjects with partial onset seizures
4. Population pharmacokinetics of YKP3089 and concomitant AEDs

6 STUDY DESIGN

6.1 Overview

This multicenter, open label study in subjects with poorly controlled partial seizures will consist of a screening period, open-label titration phase, open label maintenance phase and a taper and follow up. At least 20 subjects taking phenytoin and at least 20 subjects taking phenobarbital will be enrolled. Additional subjects taking AEDs other than phenytoin or phenobarbital, will be enrolled in order to expose at least 1,000 subjects for 6 months to further evaluate long term safety.

6.1.1 *Screening Period*

The screening period for subjects on stable doses of phenytoin or stable doses of phenobarbital or stable doses of other concomitant AEDs will be up to 21 days.

During Screening, assessments will be performed according to the study assessments listed in Table 1 to determine eligibility for the study. Each subject will be informed of his or her rights, and the subject or his or her legally authorized representative must sign an informed consent document indicating understanding of the purpose of the study and required procedures and indicating willingness to participate in the study.

6.1.2 *Open label Treatment Period*

The open label treatment period will consist of a 12 week titration phase followed by an open label maintenance phase.

6.1.2.1 *Titration Phase*

Subjects taking phenytoin or phenobarbital

The titration phase for subjects on stable doses of phenytoin or stable doses of phenobarbital will be 12 weeks. During the 12-week up-titration phase, subjects will increase YKP3089 dose every 2 weeks to a target dose of 200mg/day as described in [Table 6](#).

Table 6. YKP3089 Initial Up-Titration for subjects on phenytoin and phenobarbital

YKP3089 dose (mg/day)

To improve tolerability, the investigator may instruct the subject to take the dose of YKP3089 in the evening. The investigator may alter the timing or amount of an individual dose of any other concomitant AED, but the total daily dose and dosing frequency of any other concomitant AED must remain unchanged during the titration phase.

Subjects taking concomitant AEDs other than phenytoin or phenobarbital

The titration phase for subjects on stable doses of other concomitant AEDs will be 12 weeks. Increasing doses of YKP3089 will be administered (50, 100, 150 and 200mg/day) at 2-week intervals as described in [Table 7](#).

Table 7. YKP3089 Initial Up-Titration for subjects on concomitant AEDs other than phenytoin or phenobarbital

YKP3089 dose (mg/day)					
Week 1 & 2	Week 3 & 4	Week 5 & 6	Week 7 & 8	Week 9 & 10	Week 11 & 12
12.5	25	50	100	150	200

Prior to initiating YKP3089, subjects at US sites only will have trough concomitant AED levels (oxcarbazepine, topiramate, lamotrigine, lacosamide, clobazam, perampanel and levetiracetam only) drawn at Visit 2. Sites must instruct the subject and schedule the visit accordingly to obtain a trough level. Also the blood must be collected before first dose of YKP3089. To improve tolerability, the investigator may instruct the subject to take the dose of YKP3089 in the evening. The investigator may add, remove, or adjust the dosage of any concomitant AEDs, as clinically indicated (see [Table 8](#) below). Monotherapy with YKP3089 will not be allowed. If clinically indicated, titration can be stopped below 200mg/day. A minimum dose of 50mg/day is necessary to continue in the study.

Table 8. Dose Adjustment Rules during Titration Phase

Cohort →	Subjects taking Phenytoin or Phenobarbital	Subjects taking AEDs other than Phenytoin or Phenobarbital
Adjustments of any Concomitant AEDs	Not Allowed	Allowed
Adjustments of YKP3089	Not Allowed	Allowed

the dose of study medication in the evening or divide the total daily dose into 2 doses. Subjects will follow the schedule of study visits and assessments detailed in [Table 1](#).

After 12 months of participation in the open-label treatment period, subjects will be re-evaluated. Those who are benefiting from treatment with YKP3089 may continue use of the drug at the discretion of the investigator, until development is stopped by SK Life Science Inc or the product is approved for marketing, or anytime at the discretion of SK Life Science Inc.

Table 9. Dose Adjustment Rules during Maintenance Phase

Cohort →	Subjects taking Phenytoin or Phenobarbital	Subjects taking AEDs other than Phenytoin or Phenobarbital
Adjustments of any Concomitant AEDs	Allowed	Allowed
Adjustments of YKP3089	Allowed	Allowed
Adjustment of Phenytoin or Phenobarbital	Allowed	Not Applicable

6.1.2.3 *Taper and follow up*

Subjects who are withdrawn from the open-label treatment period will taper YKP3089 according to the schedule described in [Table 10](#), unless for safety reasons the investigator judges it necessary to discontinue study drug immediately. For subjects taking phenytoin or phenobarbital, discontinuing YKP3089 may reduce the plasma concentration of these AEDs. Doses of phenytoin or phenobarbital may need to be adjusted as clinically indicated.

Table 10. Study Drug Taper Schedule for Subjects Completing Open-Label Treatment

Final open-label dose of YKP3089 (mg/day)	YKP3089 Dose During Taper (mg/day)		
	Week 1	Week 2	Week 3
50 or 100	None		
150 or 200	100	None	None
250 or 300	200	100	None
350 or 400	300	200	100

The follow up visit will take place 14 days after the subject's last dose, following taper and discontinuation of YKP3089; at any time during the open-label treatment; or after 12 months of open-label treatment if there is no additional treatment beyond that point.

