6 STUDY DESIGN AND VISIT SCHEDULE

This is a multicenter, open label study in subjects with poorly controlled partial seizures. The study will consist of a:

- screening period,
- open-label titration phase,
- open label maintenance phase
- taper and follow up.

The study will enroll:

- Subjects on stable doses of phenytoin
- Subjects on stable doses of phenobarbital
- Subjects on stable doses of other concomitant AEDs

from approximately 80-110 sites (US and other countries)t

At least 20 subjects taking phenytoin and at least 20 subjects taking phenobarbital are to be enrolled. Additional subjects taking AEDs other than phenytoin or phenobarbital are to be enrolled in order to expose at least 1,000 subjects for 6 months to further evaluate long term safety.

Details about inclusion / exclusion criteria are included in Protocol Sections 7.3 and 7.4.

The screening period for subjects on stable doses of phenytoin or stable doses of phenobarbital or stable doses of other concomitant AEDs will be up to 21 days.

The open label treatment period will consist of a 12 week titration phase followed by an open label maintenance phase.

The titration phase for subjects on stable doses of phenytoin or stable doses of phenobarbital will be 12 weeks. During the 12-week up-titration phase, subjects will increase YKP3089 dose every 2 weeks to a target dose of 200 mg/day as described in the table below:

Table 1. YKP3089 Initial Up-Titration for subjects on phenytoin and phenobarbital

YKP3089 dose (mg/day)					
Week 1 & 2	Week 3 & 4	Week 5 & 6	Week 7 & 8	Week 9 & 10	Week 11 & 12
12.5	25	50	100	150	200

The titration phase for subjects on stable doses of other concomitant AEDs will be 12 weeks. Increasing doses of YKP3089 will be administered (50, 100, 150 and 200 mg/day) at 2-week intervals as described in the table below:

Table 2. YKP3089 Initial Up-Titration for subjects on concomitant AEDs other than phenytoin or phenobarbital

YKP3089 dose (mg/day)					
Week 1 & 2	Week 3 & 4	Week 5 & 6	Week 7 & 8	Week 9 & 10	Week 11 & 12
12.5	25	50	100	150	200

During titration phase, the investigator may add, remove, or adjust the dosage of any concomitant AEDs, as clinically indicated:

Table 3. Dose Adjustment Rules during Titration Phase

Cohort →	Subjects taking Phenytoin or Phenobarbital	Subjects taking AEDs other than Phenytoin or Phenobarbital
Adjustments of any Concomitant AEDs	Not Allowed	Allowed
Adjustments of YKP3089	Not Allowed	Allowed

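### For subjects on AEDs other than phenytoin or phenobarbital, the titration sentence lists four doses from 50 mg/day, but the table it cites has six steps from 12.5 mg/day over the stated 12 weeks

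*Protocol*

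**What the plan says.** Protocol 6.1.2 sets the length for the whole study: "The open label treatment period will consist of a 12 week titration phase followed by an open label maintenance phase". For this cohort, Protocol 6.1.2.1 repeats it: "The titration phase for subjects on stable doses of other concomitant AEDs will be 12 weeks". The next sentence reads "Increasing doses of YKP3089 will be administered (50, 100, 150 and 200mg/day) at 2-week intervals" and directs the reader to Table 7. Table 7 has six columns, from weeks 1 and 2 to weeks 11 and 12, with the doses "12.5 25 50 100 150 200" in mg/day.

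Two places in the rationale bear on the same point. Section 4.5.1 opens its plan for limiting risk with "Low starting dose (12.5 mg) and slower titration (dose increase every two weeks" and does not restrict this to one cohort. Section 4.5.2 describes two weeks at 12.5 mg, two weeks at 25 mg and then 50 mg steps for subjects on phenytoin or phenobarbital, and adds "Subjects taking concomitant AEDs other than phenytoin or phenobarbital will titrate YKP3089 upward at the same rate to a target dose of 200mg/day".

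SAP section 6 carries the same sentence, "Increasing doses of YKP3089 will be administered (50, 100, 150 and 200 mg/day) at 2-week intervals as described in the table below". The table beneath it (SAP Table 2) has the same six steps as Protocol Table 7.

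**The concern.** A dosing sentence and the table it cites should give one sequence. Here the sentence omits the two lowest steps of the table, so the two differ on the first dose a subject receives. The mismatch lies between pieces of current text in both documents; nothing here rests on the amendment log.

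Starting dose and speed of titration are the first item in the plan of section 4.5.1, which was drawn up after three DRESS cases among 953 exposed subjects. The cohort is also most of the study. The documents give no split, but if only the stated minimums of 20 phenytoin and 20 phenobarbital subjects counted towards the target of 1,000 exposed for 6 months, 1,000 − 40 = 960 would come from this cohort.

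The list cannot be dismissed at sight as a slip. Starting at 50 mg and rising by 50 mg every two weeks is a regimen with its own column in Protocol Table 5. Section 4.3.1 mentions only 50 and 100 mg tablets, whereas section 8.1.1.1 describes 12.5 and 25 mg tablets as well. In the current text, the phenytoin/phenobarbital paragraph gives a target dose and points to its table, while the paragraph for the other cohort spells out a sequence. A reader could take that as a deliberate difference between cohorts.

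**Working it through.** This is a consistency check on a schedule; no sample-size or error-rate calculation applies.

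**Inputs**
- Sentence (Protocol 6.1.2.1; SAP 6): 50, 100, 150, 200 mg/day, two weeks apart.
- Table (Protocol Table 7; SAP Table 2): 12.5, 25, 50, 100, 150, 200 mg/day, two weeks each.
- Stated duration (Protocol 6.1.2 and 6.1.2.1; SAP 6): 12 weeks.
- Visit days (Protocol section 9; SAP Appendix 1): Visit 5 = Day 43, Visit 7 = Day 71, Visit 8 = Day 85.

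**Reproducing the stated duration.** Steps × 2 weeks:
- Table: 6 × 2 = 12 weeks, which matches. Twelve full weeks end just before Day 1 + 12 × 7 = 85, the day of Visit 8.
- Sentence: 4 × 2 = 8 weeks, which is 12 − 8 = 4 weeks short. The shortfall equals the two omitted steps (12.5 and 25 mg/day) at two weeks each.

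**First dose.** 50 / 12.5 = 4.

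**Cumulative dose, days 1 to 28, if followed literally**
- Sentence: 14 × 50 + 14 × 100 = 2,100 mg.
- Table: 14 × 12.5 + 14 × 25 = 525 mg.
- Ratio: 2,100 / 525 = 4.

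**Start of 200 mg/day**
- Sentence: after 3 steps, at the start of week 7, Day 1 + 6 × 7 = 43 (Visit 5).
- Table: after 5 steps, at the start of week 11, Day 1 + 10 × 7 = 71 (Visit 7).

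**Can the list be made to fit 12 weeks?** Spreading four doses evenly needs 12 / 4 = 3-week steps, against the stated two. Holding 200 mg/day for a further 4 weeks would fill the time (8 + 4 = 12), but the section does not say so and Table 7 shows 200 mg/day only in weeks 11 and 12. Neither device removes the difference in first dose.

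**Does the list feed an analysis?** SAP 11.4 takes dosing as recorded on the eCRF and counts days at each dose level from 12.5 mg upwards. SAP 11.4.1 ends the titration phase at the Visit 9 date, the last dose or the data cut-off. No planned summary uses the four-dose list.

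**The case against.** The strongest reply is that the sentence does not stand alone. It points to a week-by-week table directly below it, and the stated 12 weeks and the 12.5 mg start in section 4.5.1 agree with that table. Drug is dispensed on IWRS instruction from Visit 2 onward, so a site does not choose bottles from this sentence alone. On this view it is a drafting slip that few readers would act on.

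Most of this stands. The conflict is confined to one list and its copy, misdosing is less likely than the fourfold figure suggests, and the documents report no instance of it. It does not remove the conflict. The IWRS schedule is not in the documents, so its agreement with either sequence cannot be assumed. Section 4.5.2 helps less than it seems: it gives this cohort the same rate and target without restating the starting dose, and 50 mg every two weeks also describes the four-dose list.

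Two stronger readings are tempting. One is that the section states two durations. It states only 12 weeks; the 8 weeks is arithmetic on the list. The other is that exposure-by-dose tables would differ according to which sequence is followed in programming. SAP 11.4 and 11.4.1 do not support that, because they use recorded doses and actual dates. An effect on deviation calls is also unproven: SAP 11.2 has deviations recorded by the monitoring CRO and listed by subject, gives no rule that refers to this sentence, and Protocol Table 8 allows YKP3089 adjustments in this cohort during titration.

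**Conclusion.** The text is wrong as written in both documents, but the error is local. The four-dose list contradicts the table it cites by a factor of four in first dose and in dose over days 1 to 28. It falls 4 weeks short of the stated 12 if each listed dose is held for one two-week step. The milligram totals describe what literal reading would give, not what subjects received.

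It should be corrected despite its small extent, because it is a current dosing instruction on the measure that the protocol names first in its hypersensitivity and DRESS plan. It does not threaten the planned exposure summaries. Agreement of other passages with the table shows where the conflict lies; it is not a judgement on which sequence is clinically right, which only the sponsor can state.

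**What to change.** Reconcile the dose sentence, Table 7 and the stated duration in Protocol 6.1.2.1, and the matching sentence and Table 2 in SAP section 6, so that one sequence and one duration appear throughout. The sponsor states which sequence applies. Check sections 4.5.1 and 4.5.2 against it in the same pass, and confirm that the IWRS dispensing schedule for this cohort matches.

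The cost is about one sentence in each document and one check of the IWRS configuration. No data collection or planned analysis needs to change on account of the wording.
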